### 2.6.3 Handling of missing values/censoring/discontinuations

For a missing individual item while on-treatment, the interpolation method using either previous or subsequent completions of the questionnaire (ACQ User Guide, 2004) will be used. For instance,

Item	Visit 1	Visit 2
1	4	6
2	3	5
3	0	0
4	4	4

5	0	0
6	2	Missing
7	5	6

Total visit 1 score for items answered on both visits is  $4+3+0+4+0+5=16$  (A)

Total visit 2 score for items answered on both visits is  $6+5+0+4+0+6=21$  (B)

Item 6 score at visit 1=2

Item 6 score at visit 2=  $B/A * 2=21/16*2=2.63$

The ACQ score for visit 1 is  $(4+3+0+4+0+2+5)/7=2.57$

The ACQ score for visit 2 is  $(6+5+0+4+0+2.63+6)/7=3.38$

For post-baseline visits, missing items will be imputed by using data from subsequent visit first, if these are not available, data from previous visit will be used for imputation of the missing item. For baseline, missing item at Day 1 will be imputed by using Day -21 data or data from any unscheduled run-in visit, whichever is later. To clarify, for imputation of the first post-baseline value, if the second post-baseline assessment is not available, the value of the baseline assessment will be used. If there are two assessments from the same day, the first will be used only and the second ignored even for imputation.

If more than one individual item is missing, then ACQ-7 score will set to be missing. The MMRM which is used for analysis of ACQ-7 score, is based on missing at random mechanism for the missing values and assesses the treatment effects of ACQ-7 without explicit imputation.

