5.6 Study completion and discontinuation

5.6.1 Study completion and post-study treatment

Completion of the study will be when the last patient has completed Visit 301 and as close as possible to safety follow-up at Day 114 for serious adverse events (SAEs).

The investigator must provide follow-up medical care for all patients who are prematurely withdrawn from the study, or must refer them for appropriate ongoing care.

5.6.2 **Discontinuation of study treatment**

Patients may voluntarily discontinue study drug (discontinue double-blind study medication but continue with study participation) at any time. Patients who wish to discontinue double-blind study medication will be asked to remain in the study and complete all study visits for

assessment of safety and vital status. Patients withdrawn from study drug will receive standard of care (SoC) asthma therapy according to investigator judgment.

The investigator should discontinue study treatment for a given patient and/or withdraw the patient from the study if, on balance, he/she believes that continuation would be detrimental to the patient's well-being.

Study treatment must be discontinued under the following circumstances:

- Patients who experience one "severe" asthma exacerbations (as defined in Section 6.4.9) during the 12 week treatment epoch that requires treatment with systemic corticosteroids or hospitalization (including intubation).
- Patients with > 50% decrease in FEV₁ from Baseline (e.g., Visit 101) confirmed by a repeat measurement the same day during the Run-in or during the treatment epoch (Baseline being then Visit 201).
- If a patient develops a medical condition that requires consistent use of prohibited treatment as per Section 5.5.8 or if patient is not compliant because of use of prohibited medications. Any other protocol deviation that results in a significant risk to the patient's
- If a patient experiences paradoxical bronchospasm, as recommended in the QMF149 **Investigator Brochure**
- Any other protocol deviation that results in a significant risk to the patient's safety.

Discontinuation of study treatment (but continued study participation)

For this study it is very important to continue collecting data, especially vital status, on all patients whether or not he/she completes treatment to continue collecting safety information. The patient should NOT be considered withdrawn from the study due to study treatment interruption or discontinuation.

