The analysis will be conducted on all patient data at the time the trial ends. Measurements made after patients discontinue randomized treatment (off-treatment measures) will not be used for any efficacy evaluation.

Any data analysis carried out independently by the investigator should be submitted to Novartis before publication or presentation.

9.1 **Analysis sets**

The following analysis sets are defined for data analysis.

The randomization (RAN) Set will consist of all patients who were assigned a randomization number, regardless of whether or not they actually received study medication.

The Full Analysis Set (FAS) will consist of all patients in the RAN set who received at least one dose of study medication. Following the intent-to-treat principle, patients will be analyzed according to the treatment they were assigned to at randomization.

The Per-Protocol Set (PPS) will include all patients in the FAS who did not have any major protocol deviations. Major protocol deviations will be defined in the statistical analysis plan prior to database lock and the unblinding of the study. Patients will be analyzed according to the treatment they received.

The Safety Set will consist of all patients who received at least one dose of study medication. Patients will be analyzed according to the treatment they received.

The FAS will be used in the analysis of all efficacy variables. The RAN set will be used for a summary of patient disposition, demographics and baseline characteristics. The PPS will be used for supportive analysis of the primary analysis only. The Safety Set will be used in the analysis of all safety variables.

Note that the FAS and Safety Sets are the same except that the Safety Set allows the inclusion of non-randomized patients who received study drug in error. Also, the FAS assigned randomized treatment and the Safety Set assigned received treatment.

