#### **2.5.4 Supportive and Sensitivity analyses**

As supportive analysis, the same MMRM used in the primary analysis will be also performed on the PPS to assess the treatment effect in protocol adherers.

In addition, the same primary MMRM on the FAS will be performed including all spirometric measures irrespective of systemic corticosteroid or rescue medication use but those measures taken outside of the 22 – 25 hour post-evening dose time window will not be included.

As a sensitivity analysis, a so-called 'tipping point analysis' will be performed for the primary endpoint to evaluate the impact of a deviation from the MAR assumption of missing data. The delta-adjusting approach described in Ratitch et al (2013) will be used to find the tipping point, in a spectrum of conservative missing not at random (MNAR) assumptions, at which conclusions change from being favorable to QMF149 to being unfavorable. After such a tipping point is determined, clinical judgment can be applied as to the plausibility of the assumptions underlying this tipping point. This methodology would provide a good picture of what it would take to overturn study conclusions on the basis of varying assumptions about missing data. The basic idea is to first impute the missing values using a regression based multiple imputation (MI) method based on the MAR assumption. The imputed Week 12 values for the QMF149 arms are then adjusted by a delta value. A detailed description of the analysis steps are provided in [Section 6.6](#).

The exploratory subgroup analyses for trough FEV1 using MMRM will be performed (using the appropriate interaction term in the model and additional covariate as a fixed effect, if necessary) for the FAS population to explore the treatment effect in key demographic and disease related subgroups (See [Section 2.2.1](#) for the details of subgroups).

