#### 2.6.4 Multiplicity adjustment

A hierarchical testing procedure will be applied to control the type-I error rate for the primary and the key secondary endpoints, i.e., the key secondary endpoint ACQ-7 will be tested only if the primary endpoint (trough FEV1) is significant at the 2-sided 0.05 level.

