## **3 Sample size calculation**

The sample size calculation takes into account the following consideration:

1. To achieve at least 90% power for the primary endpoint trough FEV1 with a treatment difference of 100 mL between QMF149 vs. MF, assuming a standard deviation of 380 mL based on internal studies CQMF149A2210, CQMF149E2201, CQMF149E2203

and literature data, where most observed treatment effects range approximately 80 mL to 120 mL.

1. To achieve at least 75% power (with multiplicity adjustment) for the secondary endpoint ACQ-7 with a treatment difference of -0.18 between QMF149 vs. MF, assuming a standard deviation of 0.80 based on study CQMF149A2210, where observed treatment difference was -0.21 with 95% confidence interval (-0.28, -0.15);

If 10% dropout rate is assumed, then calculation shows the sample size of 750 patients (ie 375/arm) will provide approximately 93% power for item 1 and 77% power for item 2 with multiplicity adjustment.

The sample size calculation was performed in PASS software.

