### **6.3 Data pooling and assessment windows**

Data from unplanned or unscheduled visits or the early treatment/study discontinuation visits will be listed. For patients who do not complete the study treatment, the treatment discontinuation visit will be an unscheduled visit.

Clinical laboratory measurements, vital signs and ECG data from unplanned or unscheduled visits will only be included in the summaries of the notable values and extreme values. All efficacy data (including spirometry data) from these visits will not be used for missing data imputation unless specified otherwise.

Laboratory, vital signs, and ECG values that have complete data and time values will be slotted into pre- or post-dose assessment based on the actual date/time. For values with missing date/time, scheduled visit date and time will be used. This rule will be applied to data from scheduled visits only. If a measurement scheduled as pre-dose is actually performed post-dose, or vice versa, the data will not be used for by time point assessments.

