4. The results for the treatment effect from the 100 datasets will then be combined using Rubin's rule. If the combined results does not change the conclusion (i.e., the QMF149 treatment effect is still statistically significantly superior to MF), a larger delta will be chosen and Steps 1-4 will be repeated using the datasets from Step 2 until the tipping point is found (when  $p > 0.05$ ).

- **Logistic regression analysis**

The analysis of proportion of patients who achieve an improvement of at least 0.5 in ACQ-7 (i.e. decrease of ACQ-7 score of at least 0.5 from Baseline) at post-baseline visits will be performed using the following steps:

1. Impute missing covariates (baseline ACQ-7, FEV1 prior to inhalation and FEV1 15 to 30 min post inhalation value) and missing continuous ACQ-7 values at Day 30 and/or Week 12 using the MI approach based on the fully conditional specification (FCS) method for 100 times and obtain 100 imputed datasets. Missing baseline ACQ-7, FEV1 prior to inhalation and FEV1 15 to 30 min post inhalation value will be imputed separately for each treatment group using a model with age group, geographic region, and the respective other covariates (baseline ACQ-7, FEV1 prior to inhalation and FEV1 15 to 30 min post inhalation value) as predictors. Missing Day 30 values will be imputed separately for each treatment group using a model with the imputed values of age group, geographic region, baseline ACQ-7, FEV1 prior to inhalation and FEV1 15 to 30 min

post inhalation value as predictors. Missing Week 12 values will be imputed separately for each treatment group using a model with the imputed values of age group, geographic region, baseline FEV1, FEV1 prior to inhalation, FEV1 15 to 30 min post inhalation, and Day 30 value as predictors.

The SAS procedure PROC MI will be used and this will result in 100 copies of the original dataset.

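### The confirmatory Week 12 ACQ-7 test assumes missing at random with no planned check of that assumption; extending the tipping-point analysis already written for trough FEV1 is a cheap improvement

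*SAP*

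**What the plan says.** **Status of the test.** SAP 2.6.4 tests ACQ-7 only if trough FEV1 "is significant at the 2-sided 0.05 level". No other secondary endpoint is in the hierarchy.

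**Missing-data assumption.** SAP 2.6.3 says of the key secondary analysis: "The MMRM which is used for analysis of ACQ-7 score, is based on missing at random mechanism for the missing values". Single missing items are filled in, but missing visits are not. The model uses baseline and the two post-baseline visits, Day 30 and Day 84.

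**Check on that assumption.** SAP 2.5.4 describes a tipping-point analysis that "will be performed for the primary endpoint to evaluate the impact of a deviation from the MAR assumption of missing data". Its steps in SAP 6.6 concern trough FEV1 at Week 12 only. The other ACQ-7 outputs stay within missing at random: the responder analysis imputes "missing continuous ACQ-7 values at Day 30 and/or Week 12 using the MI approach" under that assumption, ACQ-5 repeats the ACQ-7 methods (SAP 2.7.2), and the per-protocol set supports the primary analysis only (SAP 2.2).

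**How ACQ-7 becomes missing.** Protocol 5.6.2 requires study drug to stop after one severe exacerbation "during the 12 week treatment epoch that requires treatment with systemic corticosteroids or hospitalization (including intubation"), and after a confirmed fall in FEV1 of more than 50%. Table 5-4 has ACQ-7 at the discontinuation visit and then telephone contacts without it. Protocol Section 9 states: "Measurements made after patients discontinue randomized treatment (off-treatment measures) will not be used for any efficacy evaluation". SAP 6.3 classes the discontinuation visit as unscheduled and adds: "All efficacy data (including spirometry data) from these visits will not be used for missing data imputation unless specified otherwise".

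**The concern.** Patients stopped for a severe exacerbation or a large fall in FEV1 are stopped for something close to what ACQ-7 measures. The model has at most their baseline and Day 30 scores, and it fills the gap implicitly from similar patients who stayed on drug. A deterioration after Day 30 is invisible to it, and the score taken nearest the failure is set aside.

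The SAP accepts that a departure from missing at random deserves testing, yet tests it for only one of the two confirmatory endpoints. A significant ACQ-7 result could therefore be reported as confirmatory with nothing in the planned output to show how large a departure would overturn it. The FEV1 tipping point cannot stand in, because it is in millilitres and relates to a different effect size and a possibly different pattern of missing values.

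**Working it through.** **Inputs.** SAP 3 (repeated in Protocol 9.7): "ACQ-7 with a treatment difference of -0.18 between QMF149 vs. MF", SD 0.80; FEV1 difference 100 mL, SD 380 mL; 375 per arm; 10% dropout; stated power 93% and 77%. SAP 1.2.3: MID 0.5. SAP 2.6.4: two-sided 0.05. SAP 6.6: delta is applied to imputed Week 12 values in the QMF149 arm only.

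**1. Reproduce the stated power.** Evaluable per arm = 375 × 0.90 = 337.5.

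- FEV1: SE = 380 × √(2/337.5) = 29.25 mL; z = 100/29.25 = 3.42; power 92.8%.
- ACQ-7: SE = 0.80 × √(2/337.5) = 0.0616; z = 0.18/0.0616 = 2.92; power 83.2%.
- Both, treated as independent: 0.928 × 0.832 = 77.2%.

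These match the stated 93% and 77%, so the inputs are read correctly.

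**2. Apply the plan's delta rule to ACQ-7.** The smallest significant difference is 1.96 × 0.0616 = 0.1207. With 10% of the QMF149 arm imputed, a delta of 1.0 moves the estimate by 0.10.

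Tipping delta = (0.18 − 0.1207)/0.10 = 0.59 points, or 0.59/0.5 = 1.2 MID.

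**3. Two checks.**

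- Adding the variance that the shift itself creates, SE² = 2 × 0.80²/337.5 + 0.10 × 0.90 × delta²/375, gives a tip of 0.58 (1.16 MID).
- A simulation with 100 imputations, 37 of 375 missing per arm and an observed difference of -0.18, combined by Rubin's rules, gave p = 0.035 at delta 0.50, 0.044 at 0.55 and 0.052 at 0.60.

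**4. Two reference points.**

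- Delta 0.5 (one MID): estimate -0.18 + 0.05 = -0.13; z = 0.13/0.0616 = 2.11; p about 0.035. Still significant.
- Delta 0.18 (dropouts keep no benefit over MF): estimate -0.18 + 0.018 = -0.162; z = 2.63; p about 0.009.

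**5. Range.** Where two values appear, the lower includes the added variance of step 3.

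| Effect | Missing | Tipping delta | In MIDs |
|---|---|---|---|
| -0.15 | 10% | 0.29 | 0.6 |
| -0.18 | 10% | 0.58 to 0.59 | 1.2 |
| -0.21 | 10% | 0.87 to 0.89 | 1.7 to 1.8 |
| -0.18 | 5% | 1.19 to 1.25 | 2.4 to 2.5 |
| -0.18 | 15% | 0.37 | 0.7 |

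The effects -0.15 and -0.21 are the weaker confidence limit and the point estimate of the earlier study cited in SAP 3. The 5% and 15% rates are assumptions. At the stronger limit, -0.28, the tip would be (0.28 − 0.1207)/0.10 = 1.59.

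If only half of the missing QMF149 patients are asthma failures and only they are shifted, the tip at -0.18 and 10% is 0.593/0.5 = 1.19 points. The one-half is also an assumption.

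**The case against.** The strongest reply is that this is an optional sensitivity analysis for a secondary endpoint. The on-treatment approach is stated openly and applied to all efficacy data, and nothing in the documents requires a second tipping-point analysis. Day 30 ACQ-7 enters the model, so failure already visible at Day 30 is partly covered. Patients who stop drug are not withdrawn from the study. The delta scenario is deliberately one-sided: it worsens every missing QMF149 patient by about 3.3 times the assumed effect (0.59/0.18) and no MF patient. Other planned outputs would reveal unequal failure between arms: time to discontinuation (SAP 2.3.1), reasons for stopping (2.4.1.1) and exacerbations (2.7.6).

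Most of this stands, and it limits the point to an improvement. What remains is that none of those outputs gives a tipping delta for ACQ-7, and that the SAP's own reason for running the analysis on FEV1 applies to ACQ-7 too.

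A reader might infer that FEV1 is the sturdier endpoint and the check was put in the wrong place. At 10% missing for both, FEV1 tips at (100 − 57.3)/0.10 = 427 mL, or 1.12 SD, against 0.74 SD for ACQ-7. But SAP 2.5.3 also sets FEV1 to missing for recent rescue use, recent systemic corticosteroids or mistimed measurement, and ACQ-7 has no such rules. If FEV1 missingness were 15% (an assumption), SE = 380 × √(2/318.75) = 30.1 mL and the tip is (100 − 59.0)/0.15 = 273 mL, or 0.72 SD. The contrast then disappears, so the documents do not support the ranking.

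**Conclusion.** The gap is real and modest. One of two confirmatory tests rests on missing at random with no planned check of departures from it, in a trial where some stopping rules are tied to asthma control. On the planning figures the result would tip at about 0.6 points, slightly over one MID. This assumes an observed effect equal to the design value, an SE equal to the planning SE, 10% missing at Week 12, and delta applied to all missing QMF149 patients while MF stays at missing at random. Across the ranges shown, the tip can fall well below one MID or well above two.

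Three stronger readings do not follow:

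- **That the result falls at one MID.** At exactly 0.5 it is still significant.
- **That the planned test is biased towards QMF149 or invalid.** The share of dropout due to asthma failure and its split between arms are not given. If failures are commoner on MF, the assumption could work against QMF149.
- **That the power of the ACQ-7 test is reduced.** The planned test applies no delta, so its power is unchanged. The 56% obtained at delta 0.5 (z = 2.11) is only the chance that a sensitivity analysis at that delta stays significant.

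**What to change.** Before unblinding, amend SAP 2.6.3 and 6.6:

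1. **Correct the imputation model.** The Week 12 ACQ-7 step in the logistic-regression part of SAP 6.6 lists baseline FEV1 as a predictor where baseline ACQ-7 would be expected. Include baseline ACQ-7, so that the imputed datasets match the ACQ-7 model.
2. **Extend the tipping-point steps to Week 12 ACQ-7.** Use Day 30 in place of Day 2. Add delta to the imputed QMF149 values, because a higher score is worse. Analyse each of the 100 datasets, combine with Rubin's rules and increase delta until p > 0.05.
3. **Report** the tipping delta beside the 0.5 MID, with a row for delta = 0.18.
4. **Tabulate discontinuation-visit ACQ-7 by arm, labelled descriptive only.** It has a one-week recall, may directly follow an exacerbation and is not a Week 12 value, so it could exaggerate the departure and should not calibrate delta. The label also keeps it consistent with the bar on off-treatment efficacy data.

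The main ACQ-7 analysis stays as it is. The cost is SAP wording and some extra programming, since the imputation and delta steps are already planned, with no new visits, data or patients. The downside is that the ACQ-7 claim may have to be reported as sensitive to missing data.

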#### 2.6.4 Multiplicity adjustment

A hierarchical testing procedure will be applied to control the type-I error rate for the primary and the key secondary endpoints, i.e., the key secondary endpoint ACQ-7 will be tested only if the primary endpoint (trough FEV1) is significant at the 2-sided 0.05 level.

### 2.7 Analysis of secondary efficacy objective(s)

#### 2.7.1 Spirometry data other than the primary endpoint

Pre-dose trough is defined as the average of the two measurements taken 45 min and 15 min pre-evening dose. FEF25-75 is defined as forced expiratory flow between 25% and 75% of Forced Vital Capacity (FVC).

For all FEV1, FVC, and FEF25-75 endpoints, the baseline value is defined in a similar way as defined for trough FEV1 (See [Section 2.5.1](#)).

For FEV1, FVC and FEF25-75 measurements, missing values will be handled similarly as mentioned for trough FEV1 (See [Section 2.5.3](#)). Additionally for pre-dose trough, pre-dose measurements will be set to missing when they are actually taken post-dose. However, the post-

evening dose time window of 22 – 25 hours can not be applied here since the time of evening dose of the previous day will not be recorded. If one of the -45 and -15 min values is missing (or is not confirmed to be pre-dose) then the remaining non-missing value will be used as average pre-dose value.

Trough FEV1 at Day 2 visit will be analyzed using the same MMRM as specified for the primary analysis, i.e., the visit factor will include all available visits as a factor and between treatment comparison will be carried out using the adjusted mean (least-squares mean) difference based on the treatment main effect and the coefficient for the treatment-by-visit interaction for the respective visit and treatment. Adjusted mean (LS mean) will be displayed for each treatment group along with the estimated treatment differences and the 95% confidence intervals and the two-sided p-values by visit.

Similar analyses will be performed for pre-dose trough FEV1 at days 30 and 84.

Post-dose FEV1 (Day 1, Day 30 and Day 84) measurements will be analyzed separately by visit using the same MMRM as trough FEV1 with time point as repeat variable (i.e. in statistical model visit will be replaced by timepoint).

Pre- and post-dose FVC and FEF25-75 will be analyzed similar to FEV1 with respective baseline values (See [Section 2.1.1.2](#)).

Change from Baseline in the spirometry values will be also analyzed using the same MMRM.

For additional details of statistical models, please refer to Section 5.6.

